PROTOCOL

Background

1. Provide the scientific background, rationale and relevance of this project.

The management of septic shock has evolved since the inception of the Surviving Sepsis Campaign with short-term mortality rates improving markedly in recent years ¹. Still, the costs of survived septic shock, both financial and otherwise, are legion and include utilization of limited ICU resources, concern over growing antimicrobial resistance, ICU-delirium together with its sequelae and the morbidity associated with standard medical and ancillary care such as central-line associated blood stream infections (CLABSl).

Specifically, rates of central venous catheter (CVC) related infections are associated with increased duration of catheterization as reported in the literature and as reflected in the metric employed to track CLABSI rates, namely *rate per 1000 central line days*². Because a significant indication for CVC placement and maintenance in patients with septic shock is the requirement for intravenous (IV) vasopressors, strategies designed to shorten the duration of IV vasopressor therapy may directly impact the length of time that CVCs remain in place and, in turn, decrease CLABSI rates. Moreover, anticipated indirect effects of shortened CVC dwell times include decreased ICU length-of-stay (LOS), rate of ICU-delirium, and hospital LOS.

Midodrine is an orally available vasopressor currently FDA-approved for orthostatic hypotension. However, accumulating literature supports the use of midodrine for the purpose of decreasing intravenous vasopressor requirements in diverse ICU populations, including surgical, cardiac and medical.

Midodrine is an oral prodrug which is believed to undergo enzymatic activation to desglymidodrine, an alpha-1 receptor agonist. The prodrug has an oral bio-availability of 93% with time to peak concentration of 1 to 2 hours for the active metabolite and a half-life of 3-4 hours. Both prodrug and active metabolite are renally excreted and dialyzable. Although, as stated previously, midodrine carries FDA-approval for orthostatic hypotension, it has been used off-label for dialysis-associated hypotension and for hypotension in the ICU-setting where its use has increased 7-fold in in recent years according to one study³.

A growing body of literature comprising largely retrospective data seems to support the safety and efficacy of midodrine in the intensive care unit for decreasing IV vasopressor use³⁻⁵. In the largest retrospective case series to date, Rizvi et al. report that in 663 patients receiving IV vasopressors (in both surgical and medical ICU settings), 48% were liberated from IV vasopressor support within 24 hours of midodrine initiation. Regarding its efficacy in septic shock, Whitson et al. compared a retrospective cohort of patients in the “recovery phase” of septic shock receiving IV vasopressors and midodrine with a comparator cohort of patients receiving only IV vasopressors for the same indication. When compared with the IV vasopressor-only group, a statistically significant decrease in IV vasopressor duration approaching 24 hours was observed in the group receiving midodrine. Additionally, a decrease in ICU-LOS of nearly 2 days was

reported in the group receiving IV vasopressors and midodrine when compared with IV vasopressor-only group⁵. Finally, in a small but prospectively-designed study of 20 patients in a surgical ICU setting receiving a IV vasopressors at a mean phenylephrine equivalent rate of 41 mcg/min, the authors reported a significant acceleration in the decline rate of IV vasopressors⁶.

Importantly, complications attributable to midodrine in the above studies were minor and predominantly consisted of asymptomatic bradycardia, an expected effect of the drug. It is noteworthy that an emerging body of evidence suggests that heart rate control and relative bradycardia are associated with improved outcomes in patients with septic shock^{7,8}. Other adverse events reported have included ischemic bowel in 2 patients (0.18% of the study population), however, these events were not believed to be directly attributable to midodrine, and midodrine was only discontinued in one of these 2 patients³.

On the basis of the described, pre-existing evidence, we hypothesize that administration of midodrine in the early phase of septic shock in patients with adequate enteral access will result in a significant decrease in time to IV vasopressor liberation (increase in vasopressor-free days), secondarily resulting in decreased CVC dwell times and ICU LOS. We aim to perform a randomized, double-blind, placebo-controlled trial to investigate the efficacy of midodrine in decreasing time to IV vasopressor liberation in patients with septic shock.

Study Design: Biomedical

1. Will controls be used?

Yes

► IF YES, explain the kind of controls to be used.

The control group will receive placebo on the same schedule that the investigational agent is administered, namely every 8 hours for 72 hours. The placebo will be prepared by our investigational pharmacy and dispensed by the same.

2. What is the study design?

Randomized, Double-Blind Placebo-Controlled Trial

3. Does the study involve a placebo?

Yes

► IF YES, provide a justification for the use of a placebo

Placebo is justified to provide for blinding of the nursing staff and study investigators who might otherwise confound study results by weaning vasopressors more or less aggressively than usual practice.

Human Participants

Ages: 18-89 years of age

Sex: BOTH

Race: ANY

Subjects- see below

1. Provide target # of subjects (at all sites) needed to complete protocol.

To estimate the sample size, we used the UVA Clinical data repository (CDR) to identify 960 patients who would have met our study enrollment criteria (patients receiving IV vasopressors for >3 hours, with a diagnosis of sepsis, without cirrhosis, and not receiving midodrine). We then extracted their duration of vasopressors and the total norepinephrine equivalent doses at 24 hours. We performed repeated simulation of bootstrapped samples to estimate power from these populations with varying sample and effect sizes. Based on these estimates, we believe that a final sample size of 50 per group will provide 80% power to detect a 12-hour difference in duration of IV vasopressors based on a 2-arm study design (placebo vs midodrine). These calculations compare favorably with those obtained assuming a normal distribution, based on a mean IV vasopressor duration of 54.9 hours (SD 28.4 h) in patients with septic shock as published in a recent trial⁹, which calculations would require randomization of 49 patients to each group to detect an effect of 18 hours difference in IV vasopressor duration at a power of 80% and an alpha value of 0.05. However, because our calculations are based on internal data (and so should reflect our practices of vasopressor weaning) and because the distribution of IV vasopressor duration is non-normal, we believe that sample size calculation based upon our CDR analysis is more accurate.

To address questions regarding dosing both in terms of efficacy and safety, we will plan for an “early phase” of the study, which will essentially serve as a nested dose-response study. In this “early phase” we will randomize the first 45 subjects to one of 3 study arms (placebo, midodrine 10 mg thrice daily or midodrine 20 mg thrice daily). For the interim analysis of this “early phase”, a final sample size of 15 patients per group will provide 80% power to detect a 5 mcg/min decrease in norepinephrine equivalents at 24 hours.

Together with our “early phase” nested study and anticipating a 25% mortality in patients with septic shock we would need to enroll 115 patients to reach statistical significance. Enrolling 115 patients would allow randomization of 50 patients to placebo and 50 patients to the midodrine dose continued following the “early phase” (either 10 or 20 mg depending on the results of our interim analysis at which time we will evaluate both the safety and efficacy of both dosing strategies and continue the lowest dose that is both safe and efficacious). The additional 15 subjects would be required for the early dose-response portion of the study.

In brief:

115 total subjects: 50 placebo, 50 midodrine (either 10mg or 20mg); 15 additional subjects for the “early phase” portion of the study

2. Describe expected rate of screen failure/ dropouts/withdrawals from all sites.

Average mortality in septic shock is anticipated to be around 25-30%. Screen failure is anticipated to be around 20%, mostly due to patients with decompensated cirrhosis. This is based on our MICU septic shock database.

3. How many subjects will be enrolled at all sites?

149

4. How many subjects will sign a consent form under this UVa protocol?

149

Inclusion/Exclusion Criteria

1. List the criteria for inclusion

- Patients aged \geq 18-89 years old
- Admitted to UVA medical ICU with diagnosis of septic shock.
- Patients requiring at least 5 mcg/min norepinephrine infusion (or equivalent) for blood pressure support for at least 3 hours
- Patients with enteral access established within 12 hours of admission (either able to swallow, or feeding tube in place)

2. List the criteria for exclusion

- Pregnant females; (due to the potential adverse effects to an unborn child); patients with childbearing potential will have results of pregnancy test checked (which is routinely performed on admission); should the patient have child-bearing potential and the pregnancy status is not checked as part of routine care, such patients will be excluded from the study (i.e. pregnancy testing will not be performed for research purposes)
- Patients $<$ 18 years
- Prisoners
- Patients already taking midodrine
- Patients with cirrhosis of the liver as defined by either biopsy, imaging findings of cirrhosis AND thrombocytopenia or patients otherwise undergoing liver transplant evaluation
- Patients with Increased intraocular pressure and glaucoma
- Patients with allergy to midodrine
- Non-English speaking patients, due to the narrow time-frame for study enrollment and execution of study protocol, employing interpreters is deemed to be a significant burden on the investigators with potential to hamper study enrollment. Non-english speaking patients are not deemed to be adversely affected by exclusion from study as there is no clear *a priori* reason why study results would not also apply to non-English speakers.
- Patients without enteral access within 12 hours of initiation of IV vasopressors
- Patients where the attending physician does not clinically intend to target a mean arterial pressure of $>$ 65 mmHg
- Patients with pheochromocytoma or thyrotoxicosis
- Patients with active bowel ischemia

3. List any restrictions on use of other drugs or treatments.

Dihydroergotamines, digoxin and other cardiac glycosides. The use of drugs that stimulate alpha-adrenergic receptors (e.g., phenylephrine, pseudoephedrine, ephedrine, phenylpropanolamine or dihydroergotamine) may enhance or potentiate the pressor effects of Midodrine HCl.

Therefore, caution will be used when Midodrine HCl tablets are administered concomitantly with agents that cause vasoconstriction. However, the aim of midodrine in this trial is to potentiate vasoconstriction to treat the hypotension associated with septic shock and it will be cautiously used with phenylephrine, norepinephrine, epinephrine, vasopressin, ephedrine, or pseudoephedrine.

Although the following considerations are important when used for orthostatic hypotension these are not clinical concerns when using the agent in septic shock.

- Midodrine HCl has been used in patients concomitantly treated with salt-retaining steroid therapy (i.e., fludrocortisone acetate), with or without salt supplementation. The potential for supine hypertension exists in these patients and may be minimized by either reducing the dose of fludrocortisone acetate or decreasing the salt intake prior to initiation of treatment with Midodrine HCl.
- Alpha-adrenergic blocking agents, such as prazosin, terazosin, and doxazosin, can antagonize the effects of Midodrine HCl.

Patients will be continuously monitored in ICU and the goal of the study is to raise blood pressure.

Statistical Considerations

1. Is stratification/randomization involved?

YES

► IF YES, describe the stratification/ randomization scheme.

After enrollment, patients will initially be randomized employing a block of 9 randomization scheme generated by the study investigators. Allocation will be performed manually; there will be 5 envelopes, each envelop for a sequence of 9 patients. Each envelope will contain 3 cards for the placebo group and 3 cards for the midodrine 10 mg TID treatment group and 3 cards for the midodrine 20 mg TID treatment group. Cards will be pulled out of the envelope to randomize the patients. Once 9 patients are randomized the next envelop will be opened.

Following interim analysis of the first 45 patients, one of the treatment groups will be dropped with preference given to dropping the midodrine 20 mg TID group should interim analysis demonstrate similar, significant effect sizes in both treatment groups. Additionally, the safety profile of both dosing strategies will be considered prior to continuing the experimental arm of the study.

Subsequently, the remaining 104 patients will be randomized employing a block of 8 randomization scheme generated by the study investigators. Allocation will be performed manually; there will be 13 envelopes, each envelop for a sequence of 8 patients. Each envelope will contain 4 cards for the placebo group and 4 cards for the continuing midodrine group (either 10 mg TID or 20 mg TID). Cards will be pulled out of the envelope

to randomize the patients. Once 8 patients are randomized the next envelop will be opened.

► IF YES, who will generate the randomization scheme?

Sponsor
 UVa Statistician. Answer/Response:
 UVa Investigational Drug Service (IDS)
 Other: Answer/Response: Investigators
UVa Investigational Drug Service (IDS)

2. What are the statistical considerations for the protocol?

We will compare placebo group versus the midodrine intervention group for all primary analyses and use the Mann-Whitney U test to assess the primary outcome, which is assumed to be non-parametric.

3. Provide a justification for the sample size used in this protocol.

To estimate the sample size, we used the UVA Clinical data repository (CDR) to identify 960 patients who would have met our study enrollment criteria (patients receiving IV vasopressors for >3 hours, with a diagnosis of sepsis, without cirrhosis, and not receiving midodrine). We then extracted their duration of vasopressors and the total norepinephrine equivalent doses at 24 hours. We performed repeated simulation of bootstrapped samples to estimate power from these populations with varying sample and effect sizes. Based on these estimates, we believe that a final sample size of 50 per group will provide 80% power to detect a 12-hour difference in duration of IV vasopressors (our primary end point) based on a 2-arm study design (placebo vs midodrine). These calculations compare favorably with those obtained assuming a normal distribution, based on a mean IV vasopressor duration of 54.9 hours (SD 28.4 h) in patients with septic shock as published in a recent trial⁹, which calculations would require randomization of 49 patients to each group to detect an effect of 18 hours difference in IV vasopressor duration at a power of 80% and an alpha value of 0.05. However, because our calculations are based on internal data (and so should reflect our practices of vasopressor weaning) and because the distribution of IV vasopressor duration is non-normal, we believe that sample size calculation based upon our CDR analysis is more accurate.

To address questions regarding dosing both in terms of efficacy and safety, we will plan for an “early phase” of the study, which will essentially serve as a nested dose-response study. In this “early phase” we will randomize the first 45 subjects to one of 3 study arms (placebo, midodrine 10 mg thrice daily or midodrine 20 mg thrice daily). For the interim analysis of this “early phase”, a final sample size of 15 patients per group will provide 80% power to detect a 5 mcg/min decrease in norepinephrine equivalents at 24 hours.

Together with our “early phase” nested study and anticipating a 25% mortality in patients with septic shock would need to enroll 149 patients to reach statistical significance.

Secondary outcomes will include ICU and hospital length of stay as well as central venous catheter dwell time. Because IV vasopressor duration cannot be assumed to have a normal distribution, we intend to analyze our primary outcome using the Mann-Whitney U test.

4. What is your plan for primary variable analysis?

Dose of IV vasopressor(s) at 24 hours and hours requiring IV vasopressor therapy will be the primary outcomes of interest for the “early phase” and complete study, respectively. Because IV vasopressor duration and dose cannot be assumed to have normal distributions, we intend to analyze our primary outcome using the Mann-Whitney U test.

5. What is your plan for secondary variable analysis?

1. Central venous catheter free days
2. Hospital length of stay
3. Intravenous Vasopressor free days
4. 28-day mortality
5. ICU mortality
6. Need for re-initiation of vasopressor therapy after discontinuation for >2 hours

We will employ the Chi square test for binary outcomes. Furthermore, we will use regression analyses with appropriate interaction terms.

6. Have you been working with a statistician in designing this protocol?

No

IF YES, what is their name?

Answer/Response:

N/A

7. Will data from multiple sites be combined during analysis?

No

INSTRUCTIONS: IF YES, answer the following questions

7(a). Does the study involve randomization?

Answer/Response:

IF YES, will randomization be done at each site or among sites?

Answer/Response:

7(b). Has the sample size calculation considered the variation among sites?

Answer/Response:

7(c). When combining the data from multiple sites to assess the study results, is the effect of the treatment to be tested (or the association to be tested) assumed to be the same across sites or vary among sites? What is the modelling strategy?

Answer/Response:

7(d). Is there a common protocol used in all sites?

Answer/Response:

IF NO, how will differences among sites, such as those related to the implementation, inclusion criteria, patient characteristics, or other sites characteristics, be considered to assess the study results?

Answer/Response:

Study Procedures-Biomedical Research

1. What will be done in this protocol?

Screening:

Patients admitted to the ICU with a diagnosis of sepsis and in shock as defined, for study purposes, as requiring any IV vasopressor of at least 5 mcg/min norepinephrine infusion (or equivalent) for at least 3 hours AND with adequate enteral access (oral, orogastric, nasogastric or pre-existing PEG, will be screened by research nurse, study coordinator or study investigator by review of medical record in EPIC only. If subject meets study criteria then the research nurse, study coordinator or investigators will approach patient or surrogate for consent to participate in the study. For patients unable to provide consent due to illness, surrogate consent will be sought.

Following consent, women of childbearing potential will have a urine pregnancy test. Pregnant women will be excluded.

Study Treatment:

In the “early phase” the first 45 subjects will be randomized to one of 3 study arms (placebo, midodrine 10 mg or midodrine 20 mg thrice daily for 72 hours). The remaining 104 subjects will subsequently be randomized to one of 2 study arms, placebo or the more efficacious of the 2 midodrine doses (10 mg TID or 20 mg TID) as determined by the planned interim analysis.

Data collection from the subject’s medical record will continue until hospital discharge. Data to be collected will include the following:

1. Vasopressor(s) used by type
2. Vasopressors dose and duration
3. ICU and hospital length of stay
4. Basic lab values including CBC, makers of renal function, cardiac biomarkers (troponin, BNP)
5. Presence of central venous catheter, site and number
6. CVC dwell time

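### The target-size item gives 115 as the enrolment number after 25% mortality, but 115 contains no mortality allowance; every enrolment figure outside that item is, or sums to, 149

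*Combined protocol and SAP*

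**What the plan says.** Human Participants, item 1, answers the form's request: "Provide target # of subjects (at all sites) needed to complete protocol". It first sets the size of the main comparison: "a final sample size of 50 per group will provide 80% power to detect a 12-hour difference in duration of IV vasopressors". It then brings in the three-arm early phase and mortality together, stating that "anticipating a 25% mortality in patients with septic shock we would need to enroll 115 patients to reach statistical significance". It explains what that number buys: "Enrolling 115 patients would allow randomization of 50 patients to placebo and 50 patients to the midodrine dose continued". The remaining 15 are assigned to the early dose-response part. The In brief line repeats the figure: "115 total subjects: 50 placebo, 50 midodrine (either 10mg or 20mg); 15 additional subjects".

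The other places that state or imply an enrolment number are these:

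- Human Participants, item 3, "How many subjects will be enrolled at all sites": answered 149.
- Human Participants, item 4, "How many subjects will sign a consent form under this UVa protocol": answered 149.
- Statistical Considerations, item 3, which carries the parallel sentence with the same 25% mortality and the same early phase: 149.
- Statistical Considerations, item 1: five envelopes of nine patients for the early phase, after which "there will be 13 envelopes, each envelop for a sequence of 8 patients".
- Study Procedures, Study Treatment: 45 patients first, then a remaining 104.

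**The concern.** One sentence appears in two sections with the same premises and two different results, 115 and 149. Both cannot be the number to enrol. The version in item 1 also conflicts with its own breakdown. It says that mortality has been anticipated, yet the components are the uninflated 50 per group plus 15.

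Item 1 is where the form asks for the target size. Someone who reads only that item would believe that 115 enrolments already cover 25% mortality. An ethics reviewer, an auditor or a later reader comparing achieved with planned size could then measure the trial against the wrong figure.

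**Working it through.** **Inputs, all from the plan**

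- Power calculation: 50 per group for 80% power (Human Participants, item 1; Statistical Considerations, item 3). It comes from bootstrap simulation on internal data that the documents do not show, so it is taken as given.
- Mortality allowance: 25% (same two items).
- Additional early-phase patients: 15 (Human Participants, item 1). These correspond to the midodrine dose that is dropped. The early-phase patients in the placebo and continuing-dose arms count towards the main arms.
- Envelopes: 5 of 9 patients with 3 cards per arm, then 13 of 8 patients with 4 cards per arm (Statistical Considerations, item 1).

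**Step 1. Reproduce 115.** With no allowance, 50 + 50 + 15 = 115. This is exactly the stated figure and exactly the printed split.

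**Step 2. Apply the 25% that the sentence names.** Dividing by the surviving fraction gives n/(1 - d) = 50/(1 - 0.25) = 66.7, rounded up to 67 per continuing arm. Then 2 x 67 + 15 = 149. The documents do not print 67 or this split; both are derived here.

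**Step 3. Check against the envelopes.** The early phase has 5 x 9 = 45 patients, 5 x 3 = 15 per arm. The second phase has 13 x 8 = 104 patients, 13 x 4 = 52 per arm. The total is 45 + 104 = 149, and each continuing arm receives 15 + 52 = 67. This reaches 67 without using the mortality formula.

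**Step 4. See whether another allowance could give 115.**

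| Method | Calculation | Total |
|---|---|---|
| No allowance | 50 + 50 + 15 | 115 |
| n/(1 - d), 25%, main arms only | 2 x 67 + 15 | 149 |
| n x (1 + d), 25%, main arms only | 50 x 1.25 = 62.5, up to 63; 2 x 63 + 15 | 141 |
| n/(1 - d), 25%, the 15 inflated too | 15/0.75 = 20; 2 x 67 + 20 | 154 |
| n/(1 - d), 30%, main arms only | 50/0.70 = 71.4, up to 72; 2 x 72 + 15 | 159 |

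Only the row without an allowance gives 115. Only the 25% division applied to the two main arms gives 149.

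**Step 5. Size of the gap.** 149 - 115 = 34 patients, and 67 - 50 = 17 in each continuing arm (2 x 17 = 34).

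**The case against.** The strongest reply is that 115 and 149 answer different questions. The form asks in item 1 for the number needed to complete the protocol and in item 3 for the number enrolled. The plan calls 50 per group a final sample size. On that reading, 115 is the intended count at the end, 149 is the intake, and only the labels are wrong. As an account of what the authors meant, this is plausible. An exact completer count would depend on whether the 15 in the dropped arm are also reduced for mortality, which is a difference of a few patients, and I put no weight on it. The reading does not rescue the text, however. Item 1 describes 115 as patients to enrol, says that enrolling them permits 50 and 50 to be randomised, and attaches the mortality clause to that number.

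A second reply is that the slip is harmless, because every operating figure is 149 and a reader meets it two questions later on the same form. That largely stands, and it is why the point is of low severity.

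A reader might also infer more than the text supports. One inference is that the trial is undersized: taking 25% off 50 leaves 37.5 per arm, short of the 50 needed. That would require enrolment to stop at 115 and patients who die to leave the analysis. No section makes 115 a stopping number, and the consent, enrolment and randomisation figures all exceed it. Nor does the plan say how deaths enter the Mann-Whitney comparison of vasopressor hours. The mortality allowance hints that deaths count as losses, but the plan never states that they are excluded.

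**Conclusion.** The figure in Human Participants, item 1, is wrong as written. The 115 is the uninflated total, presented as an enrolment number that already anticipates 25% mortality. With that allowance the plan's own inputs give 149, and every enrolment figure outside item 1 is, or sums to, 149. The discrepancy is 34 patients, 17 per continuing arm.

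The consequence is limited. This is a mislabelled number in one item, with no effect on the trial as randomised and no claimed loss of power. It is also too strong to say that the planned size is unknown, since the operating figures agree with each other.

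The conclusion takes the 50 per group as given and reads the 15 as the dropped-dose arm, as item 1's own split implies. It does not depend on how deaths are handled in the analysis.

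**What to change.** In Human Participants, item 1, and its In brief line, replace 115 with 149 as the enrolment number and show the split: 67 placebo, 67 continuing midodrine, and 15 in the arm dropped after the early phase. State that 50 per group is the number the 80% power calculation assumes before the 25% mortality allowance, and that the allowance raises it to 67.

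Do not call the 50 evaluable patients, and do not imply that patients who die leave the primary analysis. The plan says neither, and such wording would write a post-randomisation exclusion into the protocol. How deaths are handled should be specified separately.

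Two optional edits could be made at the same time:

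- In Human Participants, item 1, and Statistical Considerations, item 3, describe the number as giving 80% power. A sample size does not guarantee a significant result.
- Note that Human Participants, item 2, expects mortality of 25-30%, while the allowance uses the lower end. At 30% the same method gives 159, as shown in the working.

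The cost of the main fix is wording only. The envelopes, the consent number and the randomisation totals already match 149 and do not change.

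### The 115 enrolment figure contains no mortality allowance and conflicts with 149, and 149 yields 50 evaluable per arm only at the bottom of the stated 25-30% mortality range

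*Combined protocol and SAP*

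**What the plan says.** All references are to the combined protocol and SAP.

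- **Target for the main comparison** (Human Participants, item 1; repeated in Statistical Considerations, item 3): "a final sample size of 50 per group will provide 80% power to detect a 12-hour difference in duration of IV vasopressors".
- **Total, first statement** (Human Participants, item 1): citing 25% mortality, "we would need to enroll 115 patients to reach statistical significance". The text splits this into 50 placebo, 50 on the continuing midodrine dose and 15 further early-phase subjects.
- **Total, second statement** (Statistical Considerations, item 3): "anticipating a 25% mortality in patients with septic shock would need to enroll 149 patients to reach statistical significance". Human Participants, items 3 and 4 also give 149. The randomization scheme (Statistical Considerations, item 1) and Study Procedures, item 1 split it into 45 early-phase and 104 later patients.
- **Expected mortality** (Human Participants, item 2): "Average mortality in septic shock is anticipated to be around 25-30" per cent. That item asks about dropouts and withdrawals too, but the answer gives only mortality and screen failure.
- **Early phase** (Human Participants, item 1; Statistical Considerations, item 3): "a final sample size of 15 patients per group will provide 80% power to detect a 5 mcg/min decrease in norepinephrine equivalents at 24 hours". On numbers randomized: "we will randomize the first 45 subjects to one of 3 study arms".

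The analysis text (Statistical Considerations, items 2 to 4) names the Mann-Whitney test and the outcomes. It does not say how patients who die enter either primary analysis.

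**The concern.** One premise, 25% mortality, is attached to two totals that differ by 149 - 115 = 34 patients. A reader of Human Participants, item 1 alone would take 115 as the enrolment needed for 80% power after deaths, and it is not that number.

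The 149 has a smaller problem. It is sized at the most favourable end of the protocol's own mortality range, and the 80% is then stated without that condition. The early phase states its power for a final count per group that equals the number randomized. If the trial ends without a clear difference, readers will judge it against a flat 80%, when the plan supports that figure only under particular losses.

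**Working it through.** **Inputs.** 50 evaluable per arm, 80% power, 12 hours; 15 per group at 24 hours, 80% power, 5 mcg/min; mortality 25% for sizing and 25-30% expected; 45 patients over three arms, then 104 over two. Alpha is 0.05, printed only for the normal-theory comparison; two-sided testing is assumed.

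**1. Reproduce 149.** Randomized per arm = evaluable / (1 - loss).
- 50 / (1 - 0.25) = 66.7, rounded up to 67 per continuing arm.
- 2 x 67 + 15 (the dropped dose group, not inflated) = 149.
- Check against the randomization scheme: 45/3 = 15 and 104/2 = 52, so 15 + 52 = 67 per continuing arm, and 45 + 104 = 149.
- Multiplying by 1.25 instead gives 63 per arm and 2 x 63 + 15 = 141, which does not match.

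The 149 is therefore 50 per arm inflated for exactly 25% loss.

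**2. Reproduce 115.** 50 + 50 + 15 = 115. The evaluable numbers are simply added, and the 25% appears nowhere in the sum.

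**3. Evaluable numbers from 67 per arm.** The largest loss that still leaves 50 is 1 - 50/67 = 25.4%.

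Power is approximated by Phi(2.802 x sqrt(n/50) - 1.960). Here 2.802 = 1.960 + 0.842 makes n = 50 give exactly 80%, which corresponds to an SD of 21.4 hours for a 12-hour difference.

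| Loss | Evaluable per arm | Power |
|---|---|---|
| 25% | 67 x 0.75 = 50.25 | 80.2% |
| 27% | 67 x 0.73 = 48.9 | 79.1% |
| 28% | 67 x 0.72 = 48.2 | 78.6% |
| 30% | 67 x 0.70 = 46.9 | 77.4% |

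A two-sample t calculation calibrated the same way agrees within 0.1 point. Rounding down to 46 whole patients gives 76.6%. For scale, holding 50 evaluable at 30% loss would take 50/0.70, rounded up to 72 per arm, and 2 x 72 + 15 = 159 in total.

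**4. Early phase.** 45/3 = 15 randomized per group against 15 needed, so the allowance is zero. Under the same approximation, calibrated to 80% at 15 per group, 14 with a 24-hour value give 77.2% and 13 give 74.2%. One or two losses per group is an assumption made here to show sensitivity. The documents give no 24-hour loss.

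**The case against.** Several counter-arguments carry weight.

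- **25% lies inside an approximate range, and 80% is met there.** True. Sizing at 25% is a planning choice, and the gap at 30% is under 3 points. What remains is that the condition is not stated with the power.
- **The power model is not the plan's.** The sponsor's 80% comes from bootstrapping repository data with a non-normal outcome. The approximation takes that 80% as given, and the bootstrap cannot be rerun from the documents. This stands: 77% is indicative. Nor does the printed SD of 28.4 hours show that the true power is lower still, because the plan explicitly prefers its repository data to that figure.
- **Exclusion of deaths is inferred.** Also true. The inflation makes sense only if deaths are lost to the analysis, but no section says so. If deaths were kept with an assigned rank, 67 per arm would be analysed and this shortfall would not arise in this form, though the effect size could change.
- **Item 1 asks for the number needed to complete the protocol, so 115 may mean completers.** That is plausible and supports relabelling it. As worded, however, it is an enrolment figure that claims to allow for mortality.

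Two stronger readings are tempting. A reader might infer that the trial has only about 65-68% power, because 115 enrolled with 25-30% loss leaves 37.5 to 35 per arm. The documents do not support this: the randomization scheme implements 45 + 104 = 149. A reader might also apply 25-30% mortality to the early phase, or conclude that both stages are underpowered. The 25-30% has no time horizon and is not a 24-hour rate, so the early-phase loss is unknown.

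The absence of a withdrawal rate adds little. Outcomes come from the medical record, so stopping study drug need not lose them.

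**Conclusion.** The point holds in limited form and is minor.

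- **Certain from the text:** 115 contains no mortality allowance although it cites one, and it conflicts with the 149 used everywhere that enrolment is put into operation.
- **Certain from arithmetic:** 149 leaves 50 evaluable per arm up to about 25% loss, the lower end of the protocol's own range.
- **Conditional:** if deaths are excluded and loss reaches 30%, about 47 per arm remain and power is roughly 77% instead of 80%. This rests on two-sided 0.05 and on the plan's 80% at 50 per arm being correct.
- **Open:** the early-phase 80% holds only if every randomized patient has a 24-hour value. How far it would fall short cannot be taken from the documents.

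**What to change.** 1. In Human Participants, item 1, delete 115 as an enrolment figure or relabel it as the evaluable count (50 + 50 + 15), and give 149 as the enrolment there, with 67 randomized per continuing arm.
2. In Statistical Considerations, item 3, say that 80% for the final test holds at 25% loss, and give the value at 30%: about 77%, to be confirmed by rerunning the repository simulation at 47 per arm before it is written in.
3. Say that the early-phase 80% assumes all 15 per group have a 24-hour value.
4. In the same place, state whether deaths are excluded from each primary analysis, since the inflation to 149 depends on it.

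No extra patients are needed. The cost is a few sentences, one simulation rerun and a slightly less favourable stated power.
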